### 7.2 Patient Discontinuation, Site Termination or Study Termination

#### 7.2.1 Withdrawal of Individual Patients Prior to Study Completion

Considering the retrospective study design, no withdrawal of individual patients prior to study termination is expected.

#### 7.2.2 Study or Study Site Termination

The Sponsor reserves the right, at any time, to discontinue selection of additional patients into the study, at any site; or to discontinue the study for administrative reasons.

### 7.3 Bias and Limitations of the Study

#### 7.3.1 Selection Bias

##### 7.3.1.1 Sites

Sites will be selected from hospital-based experienced medical retina centers treating DME patients as these centers will be experienced in intravitreal Ozurdex injections. Because the participating sites comprise a population of volunteers, a non-response selection bias is possible.

### **7.3.1.2 Patients**

In order to limit bias in the selection of patients, sites will attempt to consecutively select all patients who meet the selection criteria, regardless of demography or other considerations, based on date of first Ozurdex implant injection. All patients meeting the selection criteria, regardless of their selection for the study, will be identifiable in a screening log collecting minimum non-identifying patient information (see Sections 9.2 and 10.1). Characteristics of selected and non-selected patients will be compared to assess patient selection bias and reason for not being selected will be described (patient did not met selection criteria, lack of time, quotas were met, etc.).

### **7.3.2 Information Bias**

Information bias is a distortion in the estimate of association between risk factor and disease that is due to systematic measurement error or misclassification of patients on one or more variables, either risk factor or disease status. As the study is retrospective, the study will rely on data that have already been collected for another purpose (e.g. patient care). As a result, not all data to be collected in this study may be recorded in the medical charts, leading to a potential bias due to missing data. Moreover, as the study is anonymous, no queries will be issued to the sites in case of missing or incoherent data. Finally, as this is a multicenter study, the methods used to estimate the data variables collected during the chart review process may be heterogeneous across sites. This could potentially introduce a systematic bias into the results and would likely result in greater variability in the study result (e.g. OCT method used to measure CRT or method used to measure BCVA).

Information bias can be minimized by the use of electronic data capture technology. In addition to minimize the burden on the investigators and the sites, electronic data capture technology will maximize the quality and relevance of the data using automated online controls (e.g., automated controls on value ranges, units, internal consistency, and missing key data). To complement automated online controls, principal investigators will be requested to review all entered data submitted in the electronic data capture system.

### **7.3.3 Confounding Bias**

Confounding bias may result from selective prescribing of a particular treatment to more severely affected patients. As a result of a higher background risk, reported event rate may be higher and give the appearance of an elevated risk related to the use of the treatment. The collection of relevant medical information prior to first Ozurdex implant injection will help to identify the presence of elevated background risk of safety events, so that incidence of safety events can be compared through subgroup analysis to what was observed in available literature to determine whether the elevated risk is likely to be related to background risk or use of Ozurdex (e.g. previous occurrence of glaucoma, previous cataract, previous anti-VEGF treatment).

## 8 STUDY POPULATION

### 8.1 Sites

Site selection will aim to recruit qualified ophthalmologists experienced in intravitreal injections who are most likely to treat patients with DME with Ozurdex. A sample of ophthalmologists working in experienced medical retinal centers treating DME patients will thereby be selected.

### 8.2 Patients

From a public health and market access perspective, the present study population constitutes a broader real-world patient population than that reflected in clinical trials. The present study design cannot make any conclusions on causal relationships, but can rather explore real-world Ozurdex drug utilization patterns, effectiveness and safety. It is expected that the results from this study may be generalizable to the overall population presenting with DME and treated with Ozurdex in Germany and Switzerland.

Patients may contribute at most one eye into the study. If both eyes meet the inclusion criteria, the eye that received the most Ozurdex injections will be chosen as the study eye.

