### **10.6 Contralateral Eye**

DME status in the contralateral eye will be recorded at baseline and at all visits occurred during the study period.

Treatments for DME received prior to study period will be recorded for the contralateral eye. For each visit occurred during the study period, treatments received in the contralateral eye (inclusive of intravitreal treatment) will be recorded.

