## 14 STATISTICAL METHODS

### 14.1 Sample Size

The study aims to select 150 patients. As study primary objective is to assess reinjection interval of Ozurdex implant in real-world, sample size calculations were performed to evaluate the precision around the mean of the reinjection interval.

Few data were published on the reinjection interval in patients diagnosed with diabetic macular edema in real-world. Matropasqua et al. reported a mean  $\pm$  standard deviation (SD) of  $6.7 \pm 2.3$  months in 27 Italian patients. Querques et al. reported a mean of 4.9 and 4.7 months from respectively 570 French patients of a pharmacist database and 114 patients from the French Social Security database (no standard deviations were available). The same study also reported a mean ( $\pm$ SD) of  $4.8 \pm 1.8$  months between reinjections based on data from 111 French ophthalmologists who completed a survey about their practice.

The precision of the 95% confidence interval (CI) of the mean ( $\omega$ , half of the width of the CI) is determined using the following formula:

$$\omega = \frac{1.96 \times SD}{\sqrt{n}}, \text{ where SD is the standard deviation and } n \text{ is the sample size.}$$

Table 4 shows the precision and 95% CI of the mean considering a SD ranging from 1.5 to 3.0 and a sample size of 150 patients.

**Table 4 Precision and 95% CI of the mean considering a standard deviation ranging from 1.5 to 3.0, a mean ranging from 4.7 to 6.7 and a sample size of 150 patients**

SD	Mean (month)				
	$\omega$	4.7	5.5	6.0	6.7
1.5	0.2	4.5-4.9	5.3-5.7	5.8-6.2	6.5-6.9
2.0	0.3	4.4-5.0	5.2-5.8	5.7-6.3	6.4-7.0
2.5	0.4	4.3-5.1	5.1-5.9	5.6-6.4	6.3-7.1
3.0	0.5	4.2-5.2	5.0-6.0	5.5-6.5	6.2-7.2

Considering SD of the mean reinjection interval ranging from 1.5 to 3 months, the selection of 150 patients will enable the description of a mean reinjection interval with precision ranging from 0.2 to 0.5 months, i.e. 6 to 15 days (worst case).

For example, for a mean interval between two Ozurdex injections of 6.0 months, the 95% CI of the mean would be 6.0 [5.5-6.5] months in the worst case (i.e., 183 days [168-198],  $\omega = 15$  days).

 Standard deviation was not clearly available in the paper and was recalculated from available data.

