## **15.0 ANALYSES OF THE OBJECTIVES OF THE STUDY**

### **15.1 ANALYSIS OF THE PRIMARY OBJECTIVE**

The primary objective '*To assess reinjection interval of Ozurdex implants in patients with DME in real-world in Germany and Switzerland*' will be assessed by the following outcomes:

- Total number of Ozurdex reinjections in the study eye during follow-up, and considering years after the first Ozurdex injection in the study eye (See definition in Table 21-1).
- Re[injection interval defined in months as: (Date of injection (j+1) – Date of injection j) ÷ (365.25÷12), for j=1,...,n where n is the number of reinjections in the study eye. The result will be rounded to 0.1.

The number of Ozurdex reinjections in the study eye per year will be first summarized using descriptive statistics for the following parameters:

- The total number and percentage of Ozurdex reinjections received during follow-up.
- Number and percentage (with 95% CI) of patients with at least one Ozurdex reinjection during Year 1 (See definition in Table 21-1), and number of reinjections per patient during Year 1, for all patients in the analysis population. Note: the first Ozurdex injection will not be considered here, only reinjections will be counted.
- Number and percentage (with 95% CI) of patients with at least one Ozurdex reinjection and number of reinjections per patient during Year k (k=2, 3), for patients having a complete Year k of follow-up (see definition of 'Complete year' in Section 21.2).
- Number and percentage of patients receiving each Ozurdex reinjection (first, second, third, etc) for each year of follow-up (Year k, k=1 to 3) considering patients having the complete year of follow-up.

The Ozurdex reinjection interval in the study eye will be described using descriptive statistics for the following parameters:

- Re[injection interval (months) considering all eligible reinjections recorded in the EDC. The 95% CI of the mean will also be presented.
- Re[injection interval (months) considering each reinjection separately (i.e. first reinjection, second reinjection, etc). 95% CI of the mean will also be presented.

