## **22.0            CHANGES TO ANALYSES SPECIFIED IN PROTOCOL**

The changes to the analyses specified in the original protocol, dated 24 July 2018, are specified below:

In protocol Section 14.2.2.3.2 it is specified that reason of initial injection and for reinjection will be described. Reason for initial injection is not collected in the eCRF and therefore only reason for reinjection will be described.

No analyses will be performed on the contralateral eye with the exception of AESIs (Section 15.2.4) and select measures of ophthalmic history and current ophthalmic conditions (Section 10.2).

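### Where both eyes qualify, the study eye is picked by its injection count, which is itself a primary-objective outcome; this inflates reinjection counts and probably shortens the mean interval

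*Protocol*

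**What the plan says.** Protocol 8.2 limits each patient to one eye ("Patients may contribute at most one eye into the study") and then says that, when both eyes are eligible, "the eye that received the most Ozurdex injections will be chosen as the study eye". SAP 4.0 repeats the rule. Neither document says what happens when the two counts are equal.

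SAP 15.1 gives two outcomes for the primary objective:
- A count: "Total number of Ozurdex reinjections in the study eye during follow-up", with further counts by year.
- The reinjection interval, summarised by reinjection number and also pooled, "considering all eligible reinjections recorded in the EDC. The 95% CI of the mean will also be presented".

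The bias sections (Protocol 7.3, SAP 7.0) cover volunteer sites, patient selection, information bias and confounding. They do not mention the choice of eye. Protocol 8.2 expects the results to generalise to all Ozurdex-treated DME patients in the two countries.

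Protocol 10.6 says that at visits during the study period "treatments received in the contralateral eye (inclusive of intravitreal treatment) will be recorded". SAP 22.0 then states: "No analyses will be performed on the contralateral eye with the exception of AESIs", plus selected ophthalmic history.

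**The concern.** The rule maximises the first primary-objective outcome and is tied inversely to the second. Over the same observation time, the eye with more injections tends to be the eye with shorter intervals. Bilateral patients therefore tend to contribute their more intensively treated eye to a study meant to describe usual reinjection practice.

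This is bias, not sampling error. A larger sample does not reduce it, and the planned confidence interval does not allow for it. Because the SAP drops almost all contralateral-eye analyses, no planned output would reveal it.

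**Working it through.** **1. The plan's own precision.** Protocol 14.1 uses ω = 1.96 × SD / √n, with n = 150 ("The study aims to select 150 patients") and SD 1.5 to 3.0 months. One month is 30.4375 days (SAP 21.3.4).
- SD 1.5: 1.96 × 1.5 / 12.247 = 0.240 months = 7.3 days.
- SD 3.0: 1.96 × 3.0 / 12.247 = 0.480 months = 14.6 days.

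Table 4 is reproduced. Its lower figure of 6 days comes from converting the rounded 0.2 months.

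**2. Why count and interval are linked.** If an eye is observed for time T after its first injection and has N reinjections, its N intervals add up to at most T, so the mean interval is at most T/N. With equal T, the eye with larger N has the lower ceiling. The link weakens if the eyes start at different times or if treatment stops before the cut-off.

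**3. Shift in bilateral patients, first simulation.** From the documents: first injections spread over the 32 months from January 2015 to September 2017, cut-off at month 44, and means and SDs within the Table 4 ranges. Assumed: the split of variance between patients and eyes, a 2-month minimum interval, start times, the chance of stopping before each reinjection, and random tie-breaking. The comparison is with a randomly chosen eligible eye. The examples below use a mean of 6.0 months. The last two columns multiply the shift by an assumed bilateral share, which is an approximation.

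| SD; variance between patients / between eyes | Starts | Stopping | Pooled shift | × 30% | × 60% |
|---|---|---|---|---|---|
| 3.0; 20% / 50% | same | none | −0.82 mo (−25.0 d) | −7.5 d | −15.0 d |
| 2.0; 30% / 20% | same | none | −0.48 mo (−14.6 d) | −4.4 d | −8.8 d |
| 2.0; 30% / 20% | staggered | none | −0.22 mo (−6.7 d) | −2.0 d | −4.0 d |
| 2.0; 20% / 50% | staggered | 30% | −0.14 mo (−4.3 d) | −1.3 d | −2.6 d |
| 2.0; 50% / 20% | staggered | 30% | −0.08 mo (−2.4 d) | −0.7 d | −1.5 d |

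Across all 80 scenarios with no trend in interval length, the pooled mean was shorter by 0.02 to 0.82 months and the patient mean by 0.02 to 1.11 months. In two kinds of setting outside those 80 the shift vanished:
- All variation between patients, with staggered starts: +0.02 months.
- Intervals lengthening by 0.3 months per injection, with 30% stopping and staggered starts: −0.01 to +0.02 months.

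**4. Second simulation, different assumptions.** Mean 5.8 months, between-eye SD 1.3, within-eye SD 1.6, follow-up 12 to 44 months, second eye started 0 to 6 months later, between-eye correlation 0 to 0.5.
- No stopping: pooled −19 to −15 days and patient mean −23 to −17 days in bilateral patients. Scaled: 15 × 0.3 = 4.5 days up to 23 × 0.6 = 13.8 days.
- 20% stopping per reinjection: pooled −8 to −6 days and patient mean −8 to −5 days. Scaled: 5 × 0.3 = 1.5 days up to 8 × 0.6 = 4.8 days.

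**5. Against the half-width.** The total SD in step 4 is √(1.3² + 1.6²) = 2.06 months, so ω = 1.96 × 2.06 / 12.247 = 0.330 months = 10.0 days. With no stopping and correlation 0, the pooled shift reaches ω at a bilateral share of 10.0 / 19 = 53%. At correlation 0.5 it takes 10.0 / 15 = 67%. With 20% stopping it does not reach ω at any share, since 8 < 10.0.

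**6. The count.** In the same-start case with SD 2.0 and a 30% / 20% split, mean reinjections per bilateral patient rise from 4.47 to 5.00, or +0.53. With stopping the excess is about +0.8. At shares of 30 to 60% these become +0.16 to +0.32 and +0.24 to +0.48 per patient overall. The count was inflated in every run, including those where the interval shift was near zero.

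**The case against.** The rule is prespecified and objective, and it affects only patients with two eligible eyes. The study is descriptive, tests no hypothesis and disclaims causal conclusions. Taking the eye with most injections also yields more data for the per-reinjection analyses. All of that is true. It explains the rule, but it does not make the primary estimates representative.

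A reader might infer that the rule takes the shorter of two mean intervals in every bilateral patient. It does not. The eye with more injections may simply have started earlier or been treated longer, and counts can tie. In a run of the step 4 set-up at correlation 0.5, 27% of bilateral patients tied and in 6% the more-injected eye had the longer mean interval. With 20% stopping that 6% became 31%.

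A reader might also infer that the bias generally matches the CI half-width. Step 5 shows that this needs no stopping together with a high bilateral share or a small SD. Stopping cannot be set aside: SAP 21.2 ends follow-up at the first concomitant anti-VEGF or corticosteroid treatment, so the plan expects it, although neither document gives a rate.

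Repeating the analysis under another eye rule may not be fully feasible. Protocol 10.7 promises injection dates for the study eye only. Protocol 10.6 records contralateral treatments by visit from the start of the study period, with no promised dates for earlier ones. Patients whose contralateral eye was treated first are those for whom a first-treated-eye rule changes the choice, and their early injections may be undated.

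**Conclusion.** The concern holds as selection on a primary-objective outcome that the plan does not acknowledge. For the injection count up to cut-off, the direction follows from the rule itself. The link to the yearly counts, and to follow-up cut short under SAP 21.2, is looser. For the mean interval, too short is the expected direction but not a certainty.

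The documents do not fix the size. In bilateral patients, assumed values give anything from near zero to about 0.8 months pooled, which is the planned summary, or 1.1 months as a patient mean. At assumed shares of 30 to 60% the whole-sample shift is typically about 1 to 5 days with frequent stopping or staggered starts, and about 4 to 14 days without stopping. The planned half-width is 7.3 to 14.6 days. Patients with only one treated eye are unaffected. The documents do not support a single bias figure. They do support the conclusion that the reported interval should not go out with its CI alone.

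**What to change.** **If the study eye can still be defined:** use a rule that ignores the injection count, namely the first eligible eye treated with Ozurdex, chosen at random if both were first treated on the same day. This is one sentence in Protocol 8.2 and SAP 4.0, and it also removes the need for a tie rule on counts. The cost is somewhat fewer reinjections for the per-reinjection analyses.

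**If abstraction is complete:**
- Report the bilateral share. The screening log holds counts for each eye, so the share can be given for eligible patients even though SAP 9.0 says the log cannot be linked to the eCRF.
- Report the primary interval and reinjection count in patients with only one Ozurdex-treated eye. This subgroup is free of the rule, but it may differ from bilateral patients in other ways, so it is a check and not a correction.
- Repeat the primary analysis under the first-treated-eye rule only where contralateral injection dates were recorded, and say how many patients that covers.
- State the eye selection and its expected direction as a limitation in SAP 7.0, and add these analyses as an exception in SAP 22.0.

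The bilateral share and the one-treated-eye results should need no new data, provided the eCRF shows whether the other eye received Ozurdex.

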#### 8.2.1 Inclusion Criteria

A patient must meet **all** of the following criteria to be eligible for participation in the study.

1. Patient received at least two Ozurdex implants in the study eye to treat visual impairment due to DME
2. Male or female patient aged  $\geq 18$  years at time of first Ozurdex implant injection
3. First Ozurdex implant injection occurred after 1 January 2015
4. Patient was followed-up at the site for at least 12 months after the first Ozurdex implant in the study eye

#### 8.2.2 Exclusion Criteria

A patient who meets the following criteria is not eligible for participation in the study.

1. Patient received Ozurdex implants as part or during a clinical study

[REDACTED]

[REDACTED]

[REDACTED]

### **8.2.4 Minimum Required Dataset**

#### **Ozurdex Real-word Utilization (in study eye)**

- Number of Ozurdex implant injections
- Date of Ozurdex implant injections
- BCVA prior to injection time and following each Ozurdex implant
- Receipt of concomitant DME treatment in the study eye

#### **Patient characteristics**

- Age
- Gender
- Date of DME diagnosis in the study eye

#### **Other treatment**

- Prior and concomitant other intravitreal injections (if relevant)

## **9 STUDY PROCEDURES**

### **9.1 Site Selection, Enrollment and Training**

#### **9.1.1 Sampling**

Allergan will identify sites among experienced medical retina centers treating DME patients. Sites will be identified using Allergan field-based knowledge.

The study will be proposed to all the sites identified by Allergan; a recruitment mail containing the study summary, the site qualification questionnaire and a reply coupon will be sent to all these sites. If the return rate is insufficient, non-responders will be contacted by telephone to fill out the site qualification questionnaire.

The Sponsor or designee will qualify sites with sufficient resources (time, personnel, and facilities) to participate in the study. Sites will be required to obtain approval from the appropriate Independent Ethics Committee (IEC), and will be responsible for maintaining all related documents, before enrollment of any patient into the study.

Recruitment will end as soon as approximately 10 sites, 7 in Germany and 3 in Switzerland, are qualified to participate in the study.

#### **9.1.2 Site Initiation**

Sites will receive a study kit once all the necessary administrative procedures have been completed (confidentiality agreement, research contract agreement, curriculum vitae... where applicable).

The study kit contains the study protocol and the e-CRF user manual. On reception of the study kit, an initiation telephone call will be organized by Clinical Research Associates (CRA) to explain the protocol, data collection, and the practical aspects of the study.

In addition, designated study personnel will participate in a training program that will encourage consistency of process and procedures at the investigative sites and ensure collection of high-quality data for this study. All sites will be trained on the protocol, study logistics, data protection, and the electronic data capture (EDC) system. Retraining will be conducted as needed.

#### **9.1.3 Site Monitoring**

During the chart-extraction period, sites will be contacted by telephone by CRAs to follow the site identification of patients, the e-CRF completion and to answer any questions sites may have concerning data to be collected and the logistics of the study. Frequency of telephone calls will be site dependent and based on identified needs for each site. A close out call will be performed by CRAs at the end of the study. Site monitoring processes will be further detailed in the Site Management and Monitoring Plan.

## 9.2 Patient Identification and Selection Procedures

Medical charts will be screened by the investigative site personnel to identify patients who satisfy all the inclusion and none of the exclusion criteria. Once a site has been initiated, site personnel will be invited to complete a screening log with all patients who received their first Ozurdex implant injection from 1 January 2015 until 1 September 2017. Data collected in the screening log, listed in Section 10.1, will help site personnel identify eligible patients. Screening logs will be anonymized before being entered in the study database.

